Participants will be confined in the clinical unit for up to 96 hours to ensure tolerance of pyronaridine and adequate clinical response. In the event that parasitaemia is not reduced from peak parasitaemia value by approximately 10-fold during the confinement period, and/or parasite regrowth occurs (≥ 5000 parasites/mL and a 2-fold parasitaemia increase within 48 hours), rescue treatment with Riamet® will be initiated.

If participants are clinically well at the end of the 96 hour confinement, they will be discharged and monitored on an outpatient basis up to the EOS visit. Before exit from confinement, clinical trial unit

nursing staff must confirm with the Investigator if any participant requires symptom-directed physical examination prior to discharge.

The following procedures will occur prior to discharge from the clinical trial unit (96 hours):

- Perform symptom-directed physical examination if clinically indicated.
- Obtain a 12-lead ECG.
- Record vital signs.
- Collect blood samples for
 - malaria 18S qPCR,
 - drug concentration,
 - parasite viability *ex vivo* growth
- Record AEs and use of concomitant medications.

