8.1.7 ANTIMALARIAL RESCUE TREATMENTS

All participants will receive compulsory antimalarial rescue treatment with Riamet® on Day 47±2, or earlier in the following cases:

- Parasitaemia is not reduced by approximately 10-fold at the end of the 96 hour confinement period (Day 12) when compared with peak parasitaemia.
- Parasite regrowth occurs after an initial reduction in parasitaemia, with regrowth defined as ≥ 5000 parasites/mL and a 2-fold parasitaemia increase within 48 hours.
- Volunteer discontinuation/withdrawal from the study (see Section 7.2).
- Investigator's discretion in the interest of participant safety.

As qPCR results are not received in real-time, rescue may occur when these parasitaemia thresholds are presumed to have occurred.

If gametocytes are present as determined by qRT-PCR at any time point after the confinement period, a single dose of Primacin® will be administered at the Investigator's discretion. A participant's G6PD status will determine the dose of primaquine administered. If an allergy or contraindication to Riamet® or Primacin® develops, Malarone® will be administered. In the rare event that a participant cannot tolerate oral drugs, participants will be admitted to hospital and I.V. artesunate will be administered.

The following procedures will be performed prior to antimalarial rescue treatment:

- Perform symptom-directed physical examination if clinically indicated.
- Obtain a 12-lead ECG.
- Record vital signs.
- Record AEs and use of concomitant medications.
- Check participant diary cards.
- Collect blood samples for
 - haematology and biochemistry,
 - malaria 18S qPCR,
 - drug concentration
- Collect sample for parasite viability *ex vivo* growth. **NOTE only if antimalarial rescue treatment is administered prior to Day 47±2.**

Please note if a participant receives antimalarial rescue treatment after administration of pyronaridine but prior to Day 47±2, drug concentration, haematology, biochemistry and future malaria research blood collection will still be required for the full duration of the trial. Following antimalarial rescue treatment blood will be taken for 18S qPCR at the completion of Riamet and until at least one negative result is obtained.

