10.5 Data Assembly

First a master dataset will be assembled formatted according to the MMV dataset standard. (cf., "MS_IQdataset_V4_20210219.docx"). Blood concentration will be in ug/mL, total parasite levels in counts/mL, and doses in mg. Gametocyte data is in copies/uL.

Parasite data after the first administration of rescue medication is flagged by setting the IGNORE column to "Rescued". The time in hours is relative to the (first) Pyronaridine tetraphosphate administration time.

A general analysis dataset is derived from the master dataset. Gametocyte data will be converted to parasite counts following the instructions in "Analyzing RNA data by [name] Nov2017.docx". Total counts of parasites were flagged to be ignored (by setting the column IGNORE to "gametocytes") if counts of gametocytes exceeded 10% of total counts.

The viable parasites counts will be derived by multiplication of the viable fraction values with the mean parasite count at treatment administration.

A general analysis dataset is derived from the master dataset. The general analysis dataset will contain the following observations: Pyronaridine blood concentrations, total counts of parasites, as well as counts of gametocytes and viable parasite counts. In addition, dosing records for *P. falciparum* inoculation, Pyronaridine tetraphosphate administration and rescue medication administration will be defined. It is advised to define additional columns DOSELEVEL and DOSEMULT to indicate the dose amount and number of doses a participant received as covariate columns.

NLME datasets for the PK and PD modeling will be derived from the general dataset.

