11.1.2 Parasite clearance kinetics

The Parasite Reduction Ratio (PRR) and corresponding parasite clearance half-life (PCt_{1/2}) of asexual parasites is derived from the clearance rate of parasitaemia after administration of pyronaridine treatment. The analysis of PD response to investigational antimalarial therapy consists of:

- calculating the optimal parasite clearance rate (slope coefficient from the log-linear decay regression of qPCR data) for each individual, then,
- estimating dose specific parasite clearance rate and 95% confidence interval (CI) by calculating the weighted average slope estimate and corresponding standard error (SE) using an inverse-variance method.

The data used for all model selection and fitting calculations is comprised of the log₁₀ transformed geometric mean of parasitaemia per timepoint per participant up to the first timepoint all parasitaemia replicates are ND. If during initial parasite clearance there are no samples ND for a participant, the last timepoint included in the analyses will be three timepoints after the minimum observed parasitemia value. All subsequent timepoints are set to 'missing' regardless of whether parasitaemia values increased afterwards due to potential recrudescence. Sensitivity analyses may be performed using other thresholds to determine parasite clearance, for example, but not limited to, the lower limit of quantification (LOQ) (i.e. the lower limit of the reportable range) of 32 parasites/mL or limit of detection of 111 parasites/mL [1], to assess robustness of PRR estimates.

The PRR per 48 hours, PRR₄₈, for asexual parasite will be estimated using the slope of the optimal fit of the log-linear relationship of the parasitaemia decay over time from pyronaridine administration for each individual, as detailed in CTM QIMR SOP 41 and Marquart et al. [8].

Table 1: Symbols and definitions of terms used in parasite clearance analysis (Part 1)

Symbol	Definition
PRR _{48,i}	Individual specific Parasite Reduction Ratio per 48 h
PRR _{48,D}	Dose specific Parasite Reduction Ratio per 48 h
$\beta_{1,i}$	Slope coefficient of log10 parasitaemia vs. time profile for individual i
SE $_{\beta_{1,i}}$	SE corresponding to $\beta_{1,i}$ for individual i
$\bar{\beta}_{1,D}$	Dose specific average slope estimate
SE($\bar{\beta}_{1,D}$)	Weighted SE of dose specific average slope estimate
PCt _{1/2}	Parasite clearance half-life

Regression Modelling to Determine Optimal Fit

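### SAP 11.1.2 sets no cut at rescue for the PRR48 and PCt1/2 dataset, so a participant rescued before clearing can have post-Riamet samples in the pyronaridine clearance regression

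*SAP*

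**What the plan says.** SAP 11.1.2 fits each participant's log-linear decay to the "geometric mean of parasitaemia per timepoint per participant up to the first timepoint all parasitaemia replicates are ND". If no sample is ND during initial clearance, "the last timepoint included in the analyses will be three timepoints after the minimum observed parasitemia value". Points are then removed from either end by smallest p-value, down to four. A fit contributes to the dose-specific PRR48 only if p < 0.001. Neither these rules nor the definition of the PD analysis set (SAP 5.1.4) names rescue.

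The PK/PD modelling data are treated differently. SAP 10.5 states: "Parasite data after the first administration of rescue medication is flagged", and SAP 10.5.2 removes flagged records. PRR48 is a separate data flow, reported in its own PRR report (SAP 4.1.2.3).

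Post-rescue samples are planned. One trigger for rescue, in Protocol 8.1.5, reads: "In the event that parasitaemia is not reduced from peak parasitaemia value by approximately 10-fold during the confinement period". After Riamet, Protocol 8.1.7 says "blood will be taken for 18S qPCR at the completion of Riamet and until at least one negative result is obtained". Protocol 8.1.7 also allows early rescue at the investigator's discretion or on withdrawal, and Protocol 8.3.7 sends a participant who becomes SARS-CoV-2 positive in confinement home with a full antimalarial course.

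**The concern.** PRR48 and PCt1/2 are the endpoint for parasite clearance after pyronaridine. In a participant rescued before clearing, the first ND sample comes after Riamet and reflects Riamet. Applied as written, the rule takes the regression through to that sample. The effect is selective, because it falls on the weakest responders. It raises their slope and carries them past a p-value criterion that most would otherwise fail. The raised slope then enters the inverse-variance mean and the between-dose test. Cohort 1 has two participants per dose group, so one such slope is half of a group's fits.

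**Working it through.** The plan states no PRR48 value, so there is no figure to reproduce.

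**Inputs from the documents**
- qPCR pre-dose and at 4, 8, 12, 16, 20, 24, 30, 36, 42, 48, 60, 72, 84 and 96 h (Protocol 8.2.2).
- ND replicates set to 1 parasite/mL, that is log10 = 0 (SAP 11.1.1).
- Trimming steps, four-point minimum, p < 0.001, and log10PRR48 = −48 × slope (SAP 11.1.2).
- Riamet course of 60 h (Protocol 6.1.2).

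**Assumptions not in the documents**
- Baseline 10^4.2 parasites/mL, noise SD 0.25 log10, Riamet log10PRR48 2 to 4, first post-rescue sample 12 to 60 h after rescue, ND below 10 parasites/mL.

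**Step 1: who is exposed.** A 10-fold fall over 96 h is 1 log10, so log10PRR48 = 1 × 48/96 = 0.5. With a steady decline from dosing, the Day 12 trigger applies below about 0.5.

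**Step 2: one profile without noise.** Take a true log10PRR48 of 0.30.
- Slope = −0.30/48 = −0.00625 per h. Level at 96 h = 4.2 − 0.60 = 3.6.
- Rescue at 96 h, Riamet log10PRR48 of 3, next sample at 96 + 60 = 156 h: 3.6 − 3 × 60/48 = −0.15, so ND, entered as 0.
- The 15 pre-rescue points alone return 0.30.
- With the 156 h point there are 16 points: sum of times 708 h, mean 44.25 h, Sxx = 25,783, Sxy = −521.54. Slope = −521.54/25,783 = −0.02023, so log10PRR48 = 48 × 0.02023 = 0.97, with p about 0.00007.

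One ND point moves the untrimmed estimate from 0.30 to 0.97.

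**Step 3: the full algorithm with noise, rescue at 96 h.** Values are median log10PRR48 and the share meeting p < 0.001.

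| Assumptions | True | No cut | Cut at rescue |
|---|---|---|---|
| As listed above | 0.30 | 0.92–1.01; 87–100% | about 0.40; 21–28% |
| Baseline 10^4.0, SD 0.2, first sample at 60 h | 0.25 | 0.92; 99% | 0.36–0.40; 23–27% |
| Same as second row | 0.45 | 0.97; 100% | 0.48–0.49; 83–87% |
| Same as second row | 0 | 0.88–0.92; 16–100% | 1–3% pass |

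The cut value for true 0.30 is the median over all fits; medians in the other rows are among passing fits. Values with the cut still exceed the truth because the window and the passing fits are chosen by p-value. That is separate from rescue.

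**Step 4: the fallback rule in the Day 12 case.** A slow decliner has its minimum near 96 h, so the next three timepoints are mostly post-rescue. With the minimum taken before rescue, a true 0.25 is still reported at a median of 0.92, with 72–81% passing.

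**Step 5: rescue for regrowth.** After a clear nadir, the fallback rule puts post-rescue data in the set in 0–2% of runs. Estimates equal those with a rescue cut: 1.20–1.21 for true 1.2 and 1.40–1.45 for true 1.5. With a shallow nadir and early rescue, post-rescue points enter in 18–77% of runs, and the shift is small or downward (true 0.9: 0.64–0.87 against 0.88–0.89 with the cut).

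**Step 6: whether the first ND point is included.** The wording does not say. With the first sample at 60 h and Riamet log10PRR48 of 3 to 4, that sample is ND in 98–100% of runs, so leaving it out leaves only pre-rescue data and no bias. At 12 h, the Step 2 profile is at 3.6 − 3 × 12/48 = 2.85, which is detectable, so a post-rescue value stays in either way.

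**The case against.** - **The trigger may be rare.** Protocol 4.3 expects that a dose as low as 180 mg may be needed to see regrowth after initial clearance, and Cohort 1 starts at 360 mg. The rescue route the design anticipates is regrowth, which the fallback rule mostly handles. This stands. The documents give no expected number of Day 12 rescues, and a reader who inferred that every rescued participant is contaminated would be wrong.
- **An exclusion may exist elsewhere.** SAP 11.1.2 cites an SOP that is not available here, and SAP 5.1.4 allows exclusion for unspecified other circumstances. Neither states a rescue cut in the text available, so one cannot be presumed, nor ruled out.
- **Trimming might remove the post-rescue points.** It can, but for true 0.25 in Step 3, 95–98% of optimal fits kept some. Nor does the algorithm isolate Riamet's decline: the fitted values lie well below 2 to 4, so the fit blends two phases.
- **A flat profile might be read as no drug effect.** Under the plan's model, dPL/dt = GR − Kill, a flat profile means killing equals growth. Without drug effect parasitaemia would rise.
- **One participant might be said to dominate a group of two, or to reverse the dose-response.** Neither is shown. With SD 0.25, contaminated fits had a log10PRR48 SE of about 0.12 to 0.22, against 0.10 for a responder at 1.0. The weight is then (1/0.12²)/(1/0.12² + 1/0.10²) = 0.41 at most and (1/0.22²)/(1/0.22² + 1/0.10²) = 0.17 at least. It can exceed half only against fast clearers (SE 0.21 at 3.0: 0.48 to 0.75). Reversal would need a higher-dose group with a true value below about 1.1.
- **The endpoint is secondary and the fits are visible.** The primary analysis already drops post-rescue data and derives its own PRR48, individual fits are plotted, and rescue dates are listed. This lowers the severity but does not correct the rule.

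**Conclusion.** The gap is real and limited. As written, SAP 11.1.2 admits post-Riamet samples for a participant rescued before clearing: mainly a fall of less than about 10-fold by 96 h, and also early rescue by discretion, withdrawal or SARS-CoV-2. Under the stated assumptions, a true log10PRR48 of 0.30 is reported at about 0.9 to 1.0 instead of about 0.4, and the fit qualifies in about 87–100% of cases instead of 21–28%. The upward direction for Day 12 rescues held at every Riamet speed tried with the first ND point included; the size depends on the assumptions and on that inclusion. An inflated slope from a poor responder can flatten the dose-response. The primary PK/PD analysis is not affected. Should-fix, on a secondary endpoint.

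**What to change.** Add to SAP 11.1.2: *Parasitaemia collected after the first administration of rescue medication (as in Section 10.5) is excluded from the PRR48/PCt1/2 dataset; the first all-ND timepoint and the minimum are identified from pre-rescue data only, and the last eligible timepoint is no later than the last sample before rescue.*

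The cost is one sentence and a filter on rescue dates that SAP 7 already lists. The downside is that slow clearers have fewer points, wider confidence intervals and more failures at p < 0.001. In the true 0.30 case, 72–79% (100 minus 28 or 21) would drop out of the dose-specific estimate. Report the number excluded per dose alongside each PRR48, so that a weak response is not lost by omission.

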9.4.3 ANALYSIS OF THE SECONDARY ENDPOINTS

This study has three secondary endpoints.

Safety parameters:

The safety and tolerability of pyronaridine will be assessed by clinical review of the following parameters:

- AEs (including SAEs and AESIs)
- Vital signs
- 12-lead ECG
- Haematology, Biochemistry, urinalysis
- Physical examination

The analysis of this endpoint is discussed in Section 9.4.4 below.

Parasite clearance kinetics:

The parasite clearance kinetics following dosing with of pyronaridine will be determined by calculating the parasite reduction ratio over a 48 hour period (PRR₄₈) and corresponding parasite clearance half-life (PCt_{1/2}); the incidence of parasite regrowth (n and % per dose group) will be recorded.

The PRR₄₈ will be estimated using the slope of the optimal fit of the log-linear relationship of the parasitaemia decay. The optimal fit will be derived using summarised replicate parasitaemia data, which have been cleaned by dealing with potential outliers, values below the limit of detection and non-detectable values (ND). The optimal fit of the log-linear parasitaemia-by-time relationship is determined by using left and right censoring to systematically remove the potential lag phase and tail phase of the parasitaemia decay. The decay rate, estimated by the slope coefficient from the log-linear decay regression, will be calculated for each participant. The overall dose-specific PRR₄₈ will be estimated with its 95% CI by calculating the weighted average slope estimate and corresponding standard error (SE) using an inverse-variance method. Only participants who have optimal regression models with appropriate fit contribute toward the dose-specific PRR₄₈. Details will be presented in the SAP.

The parasite clearance half-life (Pt ½) will be derived from the optimal decay rate. PCt_{1/2} is a transformation of PRR₄₈ into a per hour clearance rate. Details regarding the calculation of this parameter will be presented in the SAP.

PK parameters:

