A regression modelling approach to remove potential lag and/or tail phases of the parasitaemia decay profile will be used to determine the optimal log-linear decay regression. The algorithm considers removing parasitaemia data points in an iterative process from both ends of the parasitaemia curve, i.e. a combination of right censoring (removing values from the tail phase) and left censoring (removing values from the lag phase), and uses model selection techniques to find the optimal log-linear regression.

The algorithm to obtain the log-linear decay for each participant is based on the log-linear regression detailed in Equation (1), where Time is the number of hours since administration of antimalarial treatment ($Time = 1, \dots, m$), and β_0 and β_1 are the intercept and slope estimates, respectively.

$$\log_{10} Parasitemia = \beta_0 + \beta_1 Time \quad (1)$$

Based on the parasitaemia data for each participant, the iterative algorithm to determine the optimal log-linear decay for each participant is summarised in Table 2. The iterative algorithm is continued until a minimum of four observations are available.

The optimal log-linear regression model for a participant is deemed an appropriate fit if the overall model p-value < 0.001 .

Table 1: Iteration process to determine the optimal log-linear decay curve.

Step 1: For each participant, fit the full model - fit a linear regression (as defined by Equation 1) to all m parasitaemia values of participant i

Step 2: Fit two models:

- (a) Fit linear regression model to $m - 1$ parasitaemia values, removing the first observation.
- (b) Fit linear regression model to $m - 1$ parasitaemia values, removing the last observation.

Step 3: Determine the best model of Step 2(a) and Step 2(b), defined as the model corresponding to the minimum overall model p-value.

Step 4: Of the best model defined in Step 3, repeat Step 2 and Step 3 in an iterative process until a minimum of four observations.

Step 5: Of the $m - 3$ best models selected per iteration (including the full model (Step 1)), the optimal model was defined by the minimum overall model p-value.

Estimating Participant Specific PRR

The slope and corresponding SE estimate of the optimal linear regression model is used to calculate the participant specific PRR_{48} estimate and corresponding 95% confidence interval (95% CI), as shown in Equation (2) and (3), respectively.

$$PRR_{48,i} = 10^{-48 \times \beta_{1,i}} \quad (2)$$

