$$95\% \text{ CI: } 10^{-48(\beta_{1,i} \pm 1.96 \times SE(\beta_{1,i}))} \quad (3)$$

where $\beta_{1,i}$ and $SE_{\beta(1,i)}$ are the slope and corresponding standard error of the slope parameter of the optimal linear regression model, respectively.

Estimating Dose Specific PRR (PRR_{48,D})

Of the s participants with appropriate overall fit ($p < 0.001$), the average PRR_{48} and corresponding 95% CI for each cohort is estimated by using the inverse variance method to calculate the weighted average linear regression slope ($\bar{\beta}_1$) and corresponding SE. The weighted average slope for s participants in the dose with appropriate overall fit is given by Equation (4):

$$\bar{\beta}_1 = \frac{\sum_{i=1}^s (w_i \times \beta_{1,i})}{\sum_{i=1}^s w_i}, \quad i = 1, \dots, s \quad (4)$$

where the weight is the inverse of the squared standard error, $w_l = \frac{1}{SE(\beta_{1,l})^2}$. The standard error of $\bar{\beta}_1$ is estimated as, $SE(\bar{\beta}_1) = \sqrt{\frac{1}{\sum_{l=1}^s w_l}}$.

Therefore the dose specific PRR (PRR_{48,D}) and corresponding 95% confidence interval is estimated as shown in Equation (5) and (6), respectively:

$$PRR_{48,D} = 10^{-48 \times \bar{\beta}_1} \quad (5)$$

$$95\% CI: 10^{-48 \times (\bar{\beta}_1 \pm 1.96 \times SE(\bar{\beta}_1))} \quad (6)$$

Parasite Clearance Half Life

The parasite clearance half-life (PCt_{1/2}) will be derived from the optimal decay rate. The relationship between PRR₄₈ and parasite clearance half-life (PCt_{1/2}) is a simple transformation of the PRR₄₈ as shown in Equation (7):

$$PCt_{1/2} = \log_{10}(2) \times \left(\frac{48 \text{ hours}}{\log_{10}(PRR_{48,l})} \right) = \frac{\log_{10}(2)}{-\beta_{1,l}} \quad (7)$$

where PRR_{48,i} is the parasitaemia ratio estimated over a 48-hour interval that is subsequently transformed into a per hour clearance rate.

Comparison of Dose Specific PRR₄₈

To determine whether there are differences between dose specific PRRs, an omnibus test for between group differences is used. The test is used to assess whether there are differences in the weighted mean slope of the J doses, using the test statistic shown in Equation (8),

$$Q_B = \sum_{j=1}^J w_{j.} (\bar{\beta}_{j.} - \bar{\beta}_{..})^2 \sim \chi_{J-1}^2 \quad j = 1, \dots, J \quad (8)$$

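### The PRR48 window search minimises a slope = 0 p-value and its 95% CI ignores that search, so individual intervals are too narrow, slightly without a lag and markedly if there is one

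*SAP*

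**What the plan says.** Protocol 9.4.3 wants the regression to "systematically remove the potential lag phase and tail phase of the parasitaemia decay", and SAP 11.1.2 repeats that aim: "A regression modelling approach to remove potential lag and/or tail phases of the parasitaemia decay profile will be used".

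The algorithm starts from all m points. At each step it drops either the first or the last point and keeps the better of the two fits: "Determine the best model of Step 2(a) and Step 2(b), defined as the model corresponding to the minimum overall model p-value". It goes on to a floor: "The iterative algorithm is continued until a minimum of four observations are available". Among the m − 3 fits so obtained, "the optimal model was defined by the minimum overall model p-value". Acceptance uses the same quantity: "The optimal log-linear regression model for a participant is deemed an appropriate fit if the overall model p-value" is below 0.001. The section gives no residual, curvature or lack-of-fit check.

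Equation (3) gives the participant's 95% CI as 10 to the power −48 × (slope ± 1.96 × SE), where the two inputs "are the slope and corresponding standard error of the slope parameter of the optimal linear regression model, respectively". The same slopes and SEs supply the dose-specific PRR48 (Equations 4–6) and the between-dose test (Equation 8). The only sensitivity analysis named is optional and varies the clearance threshold (32 or 111 parasites/mL), not the window rule.

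**The concern.** The aim is to find which points lie on the log-linear decay. The criterion answers a different question: how strongly the slope differs from zero. That evidence grows with the number of points and the time span as well as with straightness, so a moderate lag can be left in because removing it costs more degrees of freedom than it gains in fit.

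The interval then takes the chosen window as given. It uses a normal quantile on few degrees of freedom and allows nothing for the search.

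A lag is not far-fetched here. The SAP's own algorithm is built for one, Protocol 9.4.2 mentions one as a reason for other models, and SAP 10.6.3 provides a turnover model with delayed effect and a clearance model in which dead parasites are still counted. PRR48 and the clearance half-life are the parasite-clearance secondary endpoint. If lag differed by dose, retained lag points could make it look like a difference in killing rate.

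**Working it through.** **No figure to reproduce.** The documents give no coverage, bias, lag length, residual SD or expected PRR48 for this analysis.

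**What the p-value measures.** In a one-predictor regression on n points, t² = (n − 2)R²/(1 − R²), and the overall p-value is the two-sided p-value of t on n − 2 df. It falls as R² rises and also as n rises. A lag point goes only if the gain in R² outweighs the lost point.

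**Size of the search.** SAP 10.4.1 gives the pre-dose sample plus 14 times to 96 h, so m is at most 15 in confinement. Steps 1–5 then compare 15 − 3 = 12 windows, after 1 + 2 × 11 = 23 fits.

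**Quantile alone.** With 15 points (13 df), ±1.96 SE covers 92.8%; the t quantile is 2.16, so a correct interval is 2.16/1.96 = 1.10 times as wide. With the minimum of 4 points (2 df), ±1.96 SE would cover 81%, and the t quantile is 4.30.

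**Simulation of Steps 1–5 and Equation (3).** From the SAP: sampling times and selection rule. Assumed: start log10 4 (SAP 3.1 says only that most participants should exceed 5,000/mL), flat lag then log-linear decay, normal residuals with SD 0.1–0.2 log10. Four sets of runs:

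| Series used | True log10 PRR48 | Coverage, no lag | Coverage, 12 h lag | Coverage, 24 h lag | Estimate of a true 2.0 (12 h; 24 h) |
|---|---|---|---|---|---|
| Non-detect excluded | 1–3 | 90–93% | 59–85% | 36–68% | 1.89–1.93; 1.72–1.90 |
| Cut at assumed 10/mL, non-detect excluded | 1.5–3 | 91–93% | 59–83% | 32–48% | 1.85–1.90; 1.70–1.83 |
| Non-detect excluded | 2–3 | 91–93% | 54–71% | 29–44% | not recorded |
| Never cut | 2–3 | 91–94% | 73–82% | 39–65% | 1.91–1.94; 1.76–1.87 |

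Across the three sets that exclude the non-detect point, coverage is 54–85% at 12 h and 29–68% at 24 h. A true PRR48 of 100 would be reported as about 71–85 (10^1.85 to 10^1.93) or 50–79 (10^1.70 to 10^1.90). At least one lag point stayed in 77–98% of profiles at 12 h and 84–100% at 24 h in the first two sets.

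**What the t quantile repairs.** With no lag it lifts coverage to about 93–96%. At a 12 h lag it reaches only 68–88%, so most of that shortfall comes from the window rule.

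**Non-detect point.** SAP 11.1.1 sets non-detects to 1 parasite/mL. SAP 11.1.2 uses data up to the first all-non-detect time, which can be read as including it. With it included (assumed cut-off 10/mL), a true 2.0 with a 12 h lag gives 1.96–2.00, and with a 0–4 h lag 1.97–2.16; a true 3.0 with a 0–4 h lag gives 3.06–3.12. Coverage at true 2.0 and 12 h is still only 71–81%, and the downward bias persists at 24 h.

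**Dose comparison.** Three doses with the same true log10 PRR48 of 2.0, no between-participant variation, 2 or 6 per dose. Rejection by Equation (8) at a nominal 5%: 11–16% with no lag, 17–31% with 12 h in all doses, 22–45% with lags of 0/8/12 h, 51–83% with 0/12/24 h.

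**The case against.** A reader might infer that the plan's PRR48 is simply biased low, with coverage in some fixed poor range. The documents do not support that. They state no lag length, and Protocol 9.4.2 raises lag only as a possibility, for the primary model. With no lag or a 4 h lag, one set of runs gave coverage of 89–94%, with little or no bias. The direction of the bias depends on how the non-detect point is treated.

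A reader might also infer that the algorithm defeats its own purpose. It does not. At a given n, a smaller p-value means a higher R², so removing lag points can pay. The full window won in only 2–69% of profiles at 12 h and 1–46% at 24 h, and the average share of lag points kept was 24–84%. At a 24 h lag and true 2.0, the rule gives 1.74–1.87 (SD 0.1–0.3) against 1.59 with no trimming; with almost no noise it removes the lag exactly. The four-point window did not occur in these runs, so its quantile of 4.30 marks an extreme.

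A third inference is that the main estimator should be replaced. The method follows an SOP and a publication that I cannot see, and comparability with earlier studies has value. A lag/decay/tail segmented fit chosen by BIC largely removed the bias (means 1.99–2.07 for true 2, 2.97–3.18 for true 3), but its unadjusted interval covered only about 60–96%. Its RMSE was worse in one slow, noisy case (0.18 against 0.11 at true 1.0, SD 0.2, 12 h). The simulated truth also had the segmented model's own shape, which favours it.

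Finally, PRR48 is secondary and the general approach is descriptive. SAP 11.1.3 plots each fit, so a gross retained lag would be visible. These points limit the claim. They do not make Equation (3) a 95% interval.

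**Conclusion.** The point holds in conditional form. Two things follow from the text alone: the window is chosen and accepted by a test of slope = 0, and Equation (3) allows neither for small residual df nor for the search. The individual interval is thus too narrow even in the best case, at about 91–93% coverage.

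The larger losses, and the understated PRR48, depend on a lag of roughly 12–24 h, residual SD of 0.1–0.2 log10, and exclusion of the non-detect point. All of these are assumptions. Including that point at 1/mL removes or reverses the bias at lags of 0–12 h but leaves coverage short. The primary PK/PD model does not use this regression, allows for delayed effect, and derives its own PRR48 (SAP 10.7). The change is worth making before analysis, for a secondary endpoint.

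**What to change.** 1. In Equation (3), replace 1.96 with the t quantile on the residual df of the selected window. Preferably, use a bootstrap interval that re-runs Steps 1–5 in every resample. The bootstrap lets the interval reflect the window search; it does not by itself remove bias from retained lag points, and it was not tested in these runs.
2. Keep the minimum-p window as the main estimate, for comparability with the SOP. Pre-specify as a sensitivity analysis a lag/decay/tail segmented regression on all m points, with the presence of each segment chosen by BIC, PRR48 taken from the decay slope, and its interval also bootstrapped.
3. Report PRR48 and the dose comparison under both, so that a dose-dependent lag is not read as a dose-dependent killing rate.

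Cost: SAP wording and some R code, and no new data. Individual intervals become slightly wider (about 10% at 13 df from the quantile alone), and the segmented estimate is more variable when clearance is slow and noise is high.
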